10.3. Efficacy Evaluation for the Active Treatment Phase in the Final Analysis

All subjects entering into the Active Treatment Phase of the study will be included in the analysis. Descriptive summaries for the endpoints as listed below will be performed at each applicable study visits based on the observed data by treatment sequence.

- Complete response [REDACTED] rate for oral ulcers
- Complete response rate for genital ulcers for subjects who had genital ulcers at baseline
- Number of oral ulcers
- Number of genital ulcers
- Change from baseline in the pain of oral ulcers as measured by VAS
- Change from baseline in the pain of genital ulcers, as measured by VAS in subjects who had genital ulcers at baseline
- Change from baseline in disease activity as measured by BD Current Activity scores (BD Current Activity Form)
- Change from baseline in the BD QoL score
- Change from baseline in Behçet's Syndrome Activity Score (BSAS)
- Change from baseline in the total score of the Static Physician's Global Assessment (PGA) of skin lesions (acne-like lesions, folliculitis and erythema nodosum) of BD in subjects who had BD skin lesions at baseline

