## 9. CONCOMITANT MEDICATIONS AND PROCEDURES

### 9.1. Permitted Concomitant Medications and Procedures

The following medications will be permitted:

- Corticosteroid eye drops for BD-related or other ocular diseases are allowed at any time during this study.
- Oral/topical analgesics (lidocaine gel), chlorhexidine, used according to product prescribing information, will be allowed throughout the study except for 24 hours prior to clinic visits to avoid interference with the pain assessments of oral or genital ulcers.
- Use of topical corticosteroids for ulcers and skin disease will be allowed until the day of randomization AND/OR **after the Week 12 visit (Visit 9)** and assessments for any non-responders
  - Non-responders: subjects who fail to achieve at least a partial response ( $\geq 50\%$  improvement [reduction] in the number of oral ulcers from baseline).
- Use of colchicine will be allowed at any time **after the Week 12 visit (Visit 9)** and assessments for any non-responders (subjects who fail to achieve at least a partial response in the number of oral ulcers) or for any subjects who experience a worsening of BD (eg, arthritis, skin disease, uveitis, etc).
- Chronic medication should be dosed on a stable regimen. For medications restricted by the protocol, see [Section 7.3](#). For details about prohibited medications, see [Section 9.2](#).
- Subjects may take any medication that is not restricted by the protocol or that does not confound the efficacy and safety assessments in the study. All medications (prescription and non-prescription), treatments, and therapies taken from Visit 1 through the last visit, including the Posttreatment Observational Follow-up Phase Visit, must be recorded on the appropriate page of the eCRF. The dose, unit, frequency, route, indication, the date the medication was started, and the date the medication was stopped (if not ongoing) must be recorded.

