10.2.3. Analyses of Secondary Efficacy Endpoints

Frequency counts and percentages will be provided for categorical variables including oral ulcer complete responders at Week 12, and genital ulcer complete responders at Week 12 for subjects who had genital ulcers at baseline. The proportions of complete responders in the two study treatment groups will be compared using a 2-sided Cochran-Mantel-Haenszel (CMH) test with significance level of 0.05, controlling for stratification factors including sex (male, female) and region (Japan, Other). Subjects who have discontinued early prior to Week 12 or who do not have data at Week 12 will be regarded as non-responders at Week 12. A sensitivity analysis using LOCF approach will be performed. The complete response rate based on the approach of NRI, or LOCF or the observed data will be provided for each time point during Placebo-controlled Treatment Phase.

Similarly, the proportion of subjects with no oral ulcers or no genital ulcers following subject's first complete response during Placebo-controlled Treatment Phase will be analyzed. The subjects who have a complete response prior to Week 12 but have no oral ulcers or genital ulcers assessment following subject's first complete response through Week 12 assessment will be excluded when summarizing each endpoint. The treatment comparison will only be conducted if appropriate.

The proportion of subjects achieving an oral ulcer complete response (oral ulcer-free) by Week 6, after the start of dosing, and who remain oral ulcer free for at least 6 additional weeks during the 12-week Placebo-controlled Treatment Phase will be analyzed similarly as the complete response rate as described above. Only those subjects who are oral ulcer-free by Week 6 and remain oral ulcer free for at least 6 consecutive weeks during the 12-week Placebo-controlled Treatment Phase will be considered as a responder; otherwise, subjects will be considered as non-responders. In case an oral ulcer assessment is missing at a visit, the LOCF approach will be used to impute missing assessments up to the ET visit or the last scheduled visit on or prior to date of treatment discontinuation, whichever is later.

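### Active Treatment Phase response is summarised on observed data only, with no rule for drop-outs or for added colchicine or topical corticosteroids, so long-term response to apremilast is likely to be overstated

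*SAP*

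**What the plan says.** SAP 10.3 governs efficacy after Week 12. It states that "All subjects entering into the Active Treatment Phase of the study will be included in the analysis", and then asks for descriptive summaries at each visit "based on the observed data by treatment sequence". The listed endpoints include complete response for oral ulcers and, in subjects with genital ulcers at baseline, complete response for genital ulcers. It gives no second missing-data version and does not mention added treatment. Protocol 10.6.2 leaves the detailed methods to the SAP.

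For the first 12 weeks, SAP 10.2.3 is fuller. Subjects who stop early or have no Week 12 value "will be regarded as non-responders at Week 12". The response rate under non-responder imputation (NRI), LOCF and observed data "will be provided for each time point during Placebo-controlled Treatment Phase".

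Protocol 9.2 prohibits topical corticosteroids (for ulcers and skin disease) and colchicine through Visit 9. Protocol 9.1 then opens both. For the first: "Use of topical corticosteroids for ulcers and skin disease will be allowed until the day of randomization AND/OR" after the Week 12 visit and its assessments, for subjects who have not reached a 50% reduction in oral ulcers. For the second: "Use of colchicine will be allowed at any time" after that visit, for the same non-responders and also for subjects whose Behçet's disease worsens.

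SAP 8.5 tabulates concomitant medication by analysis period, treatment group, ATC1 level and medication name. It does not do so by visit or in relation to response.

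**The concern.** Including every entrant in the analysis set does not keep every entrant in the denominator. On observed data, a subject who has left contributes nothing to later visits. Lack of efficacy is a listed reason for discontinuation (Protocol 12, SAP 6), so those who leave plausibly respond less well than those who stay.

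Added treatment acts in the same direction. A subject who is ulcer-free while using colchicine or a topical corticosteroid counts as a complete responder, with nothing to mark the co-treatment. The placebo/30 mg sequence is the more exposed: its subjects start apremilast at Visit 9, the point from which non-responders may also start the other drugs, so the two effects cannot be separated.

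What is at stake is any statement that response is maintained to Week 64. Protocol 1.3 already describes the Phase 2 result as persistence of response in subjects who remained on treatment, and the SAP 10.3 tables would carry the same kind of statement over a longer period.

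**Working it through.** The plan gives no figure for retention, added-treatment use or response in this phase, so there is none to reproduce on this point. Its one design calculation (102 per group, difference 66, SD 144, two-sided 0.05, 90% power) reproduces at 90.3% with the noncentral t distribution and is not involved.

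**Inputs from Protocol 1.3 (Phase 2, Day 85).** Complete response was 70.9% on apremilast and 28.6% on placebo. Partial response, with the same 50% threshold as Protocol 9.1, was 89.1% and 50.0%. Of 111 subjects, 100 completed 12 weeks and continued, so 11/111 = 9.9% did not.

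**Assumed, because the documents are silent.**
- Observed complete response p: 60%, with 70.9% as an alternative.
- Share d of entrants with no value at the visit: 10% to 30%.
- Uptake u of added treatment among eligible subjects: 25% to 50%.
- Share r of those users who are ulcer-free: 50%.

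**Step 1: drop-outs counted as non-responders.** The rate on all entrants is p × (1 − d), and the gap to the observed rate is p × d.

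| d | p = 60%: rate (gap in points) | p = 70.9%: rate (gap in points) |
|---|---|---|
| 10% | 54.0% (6.0) | 63.8% (7.1) |
| 20% | 48.0% (12.0) | 56.7% (14.2) |
| 30% | 42.0% (18.0) | 49.6% (21.3) |

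This gap is never negative, but it is the distance between two counting rules and not in itself a bias.

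**Step 2: comparison with full follow-up.** If drop-outs would have responded at rate q, the overstatement is d × (p − q). With d = 20% and p = 70.9%:
- q = 0: 14.2 points.
- q = 28.6%: 0.20 × (0.709 − 0.286) = 0.085, or 8.5 points.
- q = 70.9%: zero.
- q = 80%: 0.20 × (0.709 − 0.80) = −0.018, an understatement of 1.8 points.

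Overstatement from attrition therefore requires that drop-outs do worse than those who stay.

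**Step 3: who could add treatment at Week 12.** On Phase 2 rates the eligible share e is 1 − 0.500 = 50.0% after placebo and 1 − 0.891 = 10.9% after apremilast. Of 102 randomised per group that is about 51 and 11 subjects. These are counts of eligibility, not of use.

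**Step 4: added treatment also counted as non-response.** The rate is (p − e × u × r) × (1 − d). With p = 70.9%, d = 20% and r = 50%:

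| Sequence | e | u = 25% | u = 50% |
|---|---|---|---|
| 30 mg/30 mg | 10.9% | (0.709 − 0.0136) × 0.8 = 55.6% | (0.709 − 0.0273) × 0.8 = 54.5% |
| Placebo/30 mg | 50.0% | (0.709 − 0.0625) × 0.8 = 51.7% | (0.709 − 0.125) × 0.8 = 46.7% |

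Against 56.7% in Step 1, added treatment moves the rate by a further 1.1 to 2.2 points in the first sequence and 5.0 to 10.0 points in the second.

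**The case against.** The strongest reply is that the consequence is small and partly covered.

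- **Comparability with Week 12.** A reader might infer that the Week 12 and Week 64 rates must rest on different rules. They need not: SAP 10.2.3 also plans observed-data rates through Week 12, so a like-for-like comparison exists. It does not remove selective attrition.
- **Early-termination values.** SAP 5.4 assigns them to visit windows, so a subject leaving for lack of efficacy can contribute that failing value once. Later visits still lose the subject.
- **Other tables.** SAP 6 tabulates disposition with reasons, and SAP 8.5 will show colchicine and topical corticosteroid use overall. Neither is linked to response.
- **Eligibility is not use.** A reader might take 51 versus 11 of 102 as users. The figures apply Phase 2 rates to everyone randomised and say only who could qualify. Protocol 1.1 is also reserved about how much colchicine and topical treatments achieve, so a responder who used one is not necessarily responding because of it. Against that, the sponsor's amendment justification says colchicine improves oral ulcers.
- **Stakes.** Every secondary endpoint and every step of the testing hierarchy lies at or before Week 12. The phase is descriptive, and Protocol 4.2 justifies it by long-term safety. This stands and limits the weight of the point.
- **Bias the other way.** Treating any past use as permanent failure would make one short course count through Week 64. This also stands, and the remedy has to allow for it.
- **Hidden or general text.** Part of SAP 10.3 is blacked out, so a rule there cannot be excluded. SAP 4.2.5 applies LOCF to other ulcer-count endpoints, but in the context of baseline to Week 12; if it were meant to reach further, it would conflict with SAP 10.3.

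**Conclusion.** The point holds as a modest, inexpensive improvement. On the visible text, long-term complete response rests on subjects still attending, some of whom may be using other treatment for ulcers, and no planned table shows how much that matters. The rate credited to apremilast is likely to be overstated, more so in the placebo/30 mg sequence.

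The firmer claim that it will be overstated is not supported. It is certain only relative to a rule that counts drop-outs and co-treated subjects as failures. As an estimate of what full follow-up on apremilast alone would show, it needs drop-outs to do worse than those who stay, or the added drugs to work. The illustrative 6 to 18 points depend on an assumed 60% rate and an assumed 10% to 30% drop-out; the added-treatment figures depend on assumed uptake and response. The primary analysis, the Week 12 secondary endpoints and the sample size are not affected.

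**What to change.** In SAP 10.3, keep the observed-data table and add the following beside it:

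- **(a)** Oral and genital complete response rates by visit and treatment sequence, with all subjects entering the Active Treatment Phase as denominator (for genital ulcers, those with genital ulcers at baseline). Count missing values as non-response, continuing the NRI approach of SAP 10.2.3.
- **(b)** A sensitivity version of (a) that also counts as non-response any visit with use of colchicine or of topical corticosteroids for ulcers. State in advance how earlier use that has stopped is treated.
- **(c)** The number of subjects observed and the number using each added treatment, by visit and treatment sequence.

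It would also help to state that the LOCF sentence in SAP 4.2.5 applies through Week 12 only, if that is the intent.

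The data are already collected: Protocol 9.1 requires medication, indication, and start and stop dates to be recorded. No clinical rule changes. The cost is SAP wording, a few more descriptive tables and a less favourable long-term rate.

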10.4. Subgroup Analysis

The focus of subgroup analyses will be limited to the stratification factor and baseline characteristics as listed below and will be conducted on the ITT population for AUC₈₅:

- Sex (male, female)
- Race (White, non-White)
- Age (< 40, \geq 40 to < 65, \geq 65 years years)
- Region (Japan, Other; Europe, North America, Asia, Rest of the World)
- Baseline weight category (< 50, \geq 50 to < 60, \geq 60 to < 70, \geq 70 to < 85, \geq 85 kg)
- Baseline BMI category (< 18.5, \geq 18.5 to < 25, 25 to < 30, \geq 30 kg/m²)
- Alcoholic beverage intake (yes, no)
- Tobacco use (current user, past user, never user).
- Duration of disease (\leq 2, > 2 to \leq 6, > 6 to \leq 10, > 10 years)
- Baseline oral ulcers category (\geq 2 to \leq 5, > 5 to \leq 10, \geq 10)
- Prior use of colchicines (Yes, No)
- Prior use of oral corticosteroids (Yes, No)

The consistency of the treatment effect across subgroups will be assessed in the context of the primary methods used for the analyses. For AUC₈₅, sex or region will not be included as a factor for the sex or region subgroup analysis, respectively, in the ANCOVA model.

Forest plots will be provided based on the treatment differences for each subgroup estimated as described above for AUC₈₅.

10.5. Assessing Study Center Effect and Treatment-by-Center Interaction

This study is a multicenter study. As site enrollment caps are imposed in this study, no single site will have a sufficient number of subjects felt to allow a meaningful within-site analysis of treatment differences in AUC₈₅ stratified by sex, therefore, study site effects will be assessed by pooling sites on a geographic basis to help interpret the results should potential site effects be suspected. In pooling sites for analysis purposes, values around 5 are often chosen as the minimum cell size in models containing interaction terms for a continuous endpoint. In this study, a minimum of 5 ITT subjects per treatment group per stratum of sex is chosen. The detailed pooling strategy for the stratified analyses is described in 4 steps as follows:

- Sites will first be pooled within each country according to their rank based on site-specific sample size, starting with the smallest sites; i.e., within a country, the smallest sites will first be pooled until the pooled site has a minimum cell size of 5.
- The remaining unpooled sites will then be pooled within a region (as defined in the subgroup analysis by region) in a similar fashion.
- The remaining unpooled sites will then be pooled across regions in a similar fashion.

- The remaining unpooled sites will finally be pooled with the smallest pooled site.

Study site effects will be assessed for the primary efficacy endpoint by stratifying the analysis based on both sex and pooled sites and examining whether the treatment differences, adjusted for pooled site, are consistent with those from the primary analysis.

In addition, the consistency of the treatment effect across pooled sites will also be assessed by performing a subgroup-type analysis with respect to the primary endpoint, with pooled sites treated as subgroups (see Section 10.4). A table summarizing AUC_{85} values by multiple imputation approach will be provided by individual study site and treatment group.

CELGENE PROPRIETARY INFORMATION

11. SAFETY ANALYSES

11.1. General Approaches to Safety Analyses

Safety analyses will be performed for both the placebo-controlled and apremilast-exposure periods (see Section 5.2), based on the safety population and the apremilast subjects as treated population respectively. Summary tables during the placebo-controlled period are presented by treatment group, Placebo and 30 mg BID. During the apremilast-exposure period, data are presented by treatment sequence, i.e., Placebo/30 mg BID, 30 mg BID as Initiated, and a total column of 30 mg BID as Treated.

Unless otherwise specified, the analyses of AEs and marked abnormalities (laboratory parameters and vital signs) for both the placebo-controlled and apremilast-exposure periods will include the subject incidence rate (i.e. percentage [%] used in a frequency summary), which is defined as the number of subjects with the specific event divided by the number of subjects included in the analysis. Subjects with multiple occurrences of the specific event in the specific analysis period will be counted only once in the numerator.

To account for the different exposure to the IP, AEs and laboratory marked abnormalities will also be analyzed using exposure-adjusted incidence rate (EAIR) per 100 subject-years as defined below:

- The EAIR per 100 subject-years is defined as 100 times the number of subjects with the specific event divided by the total exposure time (in years) among subjects included in the analysis. Subjects with multiple occurrences of the specific event in the specific analysis period will be counted only once in the numerator. The exposure time for a subject without the specific event is the treatment duration, whereas the exposure time for a subject with the specific event is the treatment duration up to the start date (inclusive) of the first occurrence of the specific event. The total exposure time in years is calculated by dividing the sum of exposure time in days over all subjects included in the analysis by 365.25. The EAIR per 100 subject-years is interpreted as the expected number of subjects with at least one occurrence of the specific event per 100 subject-years of exposure to the study drug.

Summaries of vital signs, weight, and laboratory parameters over time (e.g., summary statistics of observed value and changes from baseline and shifts from baseline to post-baseline time points in terms of normal/abnormal or grade) will be provided. In summaries for a post-baseline time point, subjects who have both values at baseline and at the time point will be included; for end of period and shifts from baseline to the end of period and to the worst post-baseline value, subjects who have a baseline value and at least one post-baseline value will be included.

Safety data collected during the optional Open-Label Extension Phase will be listed.

11.2. Adverse Events

AEs will be classified using the MedDRA. Unless otherwise specified, AEs will be summarized by system organ class (SOC) and preferred term (PT), with SOCs presented in the standard international order and PTs within each SOC in descending order of subject incidence.

A subject data listing of all AEs (including TEAEs and non-TEAEs) sorted by subject ID and AE start date will be provided based on the safety population, irrespective of analysis periods; this listing will include a “non-treatment-emergent” flag and the date of the last IP dose. Only TEAEs will be included in the AE summaries as described below.

11.2.1. Overall Summary of Adverse Events

An overall summary of the following AE categories will be provided:

- Subjects with any TEAE
- Subjects with any drug-related TEAE
- Subjects with any severe TEAE
- Subjects with any serious TEAE
- Subjects with any serious drug-related TEAE
- Subjects with any TEAE leading to drug interruption
- Subjects with any TEAE leading to drug withdrawal
- Subjects with any TEAE leading to death

Specific TEAEs under each of the above categories will be summarized.

11.2.2. All TEAEs

All TEAEs will be summarized by

- SOC and PT
- PT only (in descending order of subject incidence)

New events of all TEAEs by exposure interval (≤ 1 , > 1 to ≤ 2 , > 2 to ≤ 4 , > 4 to ≤ 8 , > 8 to ≤ 12 and > 12 weeks) will be summarized for the placebo-controlled period and for the apremilast-exposure period (≤ 1 , > 1 to ≤ 2 , > 2 to ≤ 4 , > 4 to ≤ 8 , > 8 to ≤ 12 , > 12 to ≤ 16 , > 16 to ≤ 28 , > 28 to ≤ 40 , > 40 to ≤ 52 , > 52 to ≤ 64 and > 64 weeks); an event with a start date falling within an exposure interval is considered a new event for that interval. Each subject is counted once in the numerator of a subject incidence or EAIR for each applicable specific TEAE in each exposure interval where an event started. The denominator of a subject incidence is the number of subjects with treatment duration exceeding the lower bound of the particular exposure interval, while the denominator of an EAIR is the sum of the exposure time during the exposure interval (up to the first event start date subjects with at least one event starting in the interval) among the same number of subjects as in the denominator of the responding subject incidence.

11.2.3. Common TEAEs

TEAEs with subject incidence $\geq 5\%$ in any treatment group will be summarized by SOC and PT as well as by PT only in descending order of subject incidence.

Summaries about the most frequent TEAEs will include onset day of the most frequent TEAE, and the duration of those most frequent TEAE. The most frequent TEAEs will be those identified in the $\geq 5\%$ summaries noted above.

11.2.4. Drug-related TEAEs

Drug-related TEAEs will be summarized by SOC and PT.

11.2.5. TEAEs by Maximum Severity

All TEAEs will be summarized by maximum severity (mild, moderate, and severe). If a subject reports multiple occurrences of a specific event within a specific analysis period, the subject will be counted only once by the maximum severity.

11.2.6. Serious TEAEs

Serious TEAEs and serious drug-related TEAEs will be summarized by SOC and PT. Serious TEAEs will also be summarized by PT only (in descending order of subject incidence).

A subject data listing of all serious AEs (both TEAEs and non-TEAEs) will be listed.

